9.3. Population Analyses

The following key populations are defined. Any further population definitions will be detailed in the RAP:

Population	Definition / Criteria
Intent-To-Treat - Exposed (ITT-E)	 All assigned patient participants who received at least one dose of study treatment. This population will be based on the treatment the subject was randomized to (All subjects were assigned to the same drug regimen in this study)
	 Any participant who receives a participant number will be considered to have been assigned.
Safety	 All assigned participants who received at least one dose of CAB Oral + RPV Oral or CAB LA + RPV LA. All patients receive the same drug regimen, CAB LA + RPV LA

9.4. Statistical Analyses

There will be two main reporting and analysis timeframes. First, will be the primary complete analyses which will be conducted when the last study participant has completed their CAB LA + RPV LA study treatment up to Dose 7. All study staff participant (site-level) questionnaire and interview data, plus all study participant (subject-level) data will be included in this reporting and analysis effort.

Once all study participants have completed the study, final analyses of the data will also be conducted

The statistical analysis plans will be finalized prior to DBL and it will include a more technical and detailed description of the statistical analyses described in this section. This section is a summary of the planned statistical analyses of endpoints. Analysis on patient

study participant data will account for sites that patients are nested in. The reporting analysis plan will provide further details of the analyses.

As mentioned above, this study has both site- and subject-level outcomes and each outcome will be analyzed and summarized accordingly.

Qualitative interview data will be summarized by a third party and reported as part of the overall study results (CSR). Details of these analyses will be described in a separate analysis plan provided by the CRO partner under GSK's oversight.

Qualitative Analytic Strategy and Data Integration. The EPIS-informed qualitative data collected from both the study staff participants and the providers are embedded within the quantitative outcome of the study for expansion, development, and convergence. All qualitative data will be recorded, transcribed, translated if necessary, cleaned. Data will be entered into a qualitative data management software and any notes from calls made to study staff team that are related to study outcomes will be compiled and analyzed. The Clinical Research Organization or an identified expert consultant will be responsible for coding all qualitative assessments for use in the evaluation of feasibility, acceptability, appropriateness, barriers and facilitators of future implementation, and potential modification suggestions to implementation strategies. Established procedures to enhance validity will be used, including development of an audit trail documenting analytical decisions. All coding decisions will be noted for further review. Rater agreement will be reported. We will also use a check-coding model where the primary coder will code and recode a percentage of the same material to ensure there is over a 90% consistency.

A theory-driven approach to explore the relationship between the findings and the EPIS framework will be followed. The goals, objectives and key research questions will guide all aspects of the qualitative analyses. Using content analysis, we will identify analytical categories to describe and explain observations. Our work will occur in five stages outlined in Mays et al. framework approach to qualitative analysis: 1) Familiarization, 2) Identifying a Thematic Framework, 3) Indexing, 4) Charting, and 5) Mapping and Interpretation. Codes will be derived deductively by identifying categories at the beginning of the research (e.g., elements of the EPIS framework) and inductively by identifying those that emerge gradually from the data. Operational definitions of each code will be used and through constant comparison, updates to the coding model will occur throughout to support efforts to index the data and lead to further refinement. In the charting and mapping phases, we will integrate the qualitative and quantitative data for expansion, development, and convergence, and based on our research questions, themes, commonalities and variations in themes, and findings related to training, feasibility, acceptability, and fidelity-related issues will be examined. Data integration will assist a fine-grained understanding of processes and characteristics that may influence effectiveness and implementation outcomes of CAB LA+ RPV LA in sites across Europe.

9.4.1. Primary Endpoint(s)

[figure not shown]
Endpoint	Statistical Analysis Methods
Staff Study Participants (SSP): Change from baseline at Month 12 in Acceptability of Intervention Measure (AIM), Intervention Appropriateness Measure (IAM), and Feasibility of Intervention Measure (FIM)	Acceptability of Implementation Measure (AIM), Implementation Appropriateness Measure (IAM), and Feasibility of Implementation Measure (FIM) will be summarized using descriptive statistics including 95% confidence intervals. Data will be summarized by month of study/injection visit and by implementation strategy as actual values and change from baseline. Mean AIM, IAM and FIM scores will be compared between the two implementation arms. In addition, distribution of AIM, IAM and FIM items scores will also be compared. P-values will be reported for these comparisons.
	Responses will also be summarized overall and by site type. Exploratory analyses will be undertaken to assess the variability of responses by factors including but not limited to site type, setting and for subject level outcomes markers of demographic and baseline characteristics.

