- Month 12: within 4 weeks of the first patient receiving their last injection (Dose 7) at the site.

Qualitative interviews will be conducted with study staff participants and to assess whether acceptability, appropriateness, fidelity, and sustainability are achievable within each site's setting. Interviews will probe for multilevel barriers to, and facilitators of, CAB LA+RPV LA implementation. Key stakeholder interviews will elicit in-depth information as these individuals have first-hand knowledge of the factors influencing local implementation. The interviews are EPIS-based (Aarons, 2011) which allows for information about characteristics of the adopters, needs and resources of each site, impact of leadership, and factors that might impact the larger system including policy changes at a local and national level.

The interviews for staff study participants will be conducted with up to approximately 4 participants of various disciplines in each clinic that play a critical role (e.g., HIV care providers, nurse/person(s) administering the injections, clinic administrator/manager(s), pharmacists).

An example of a baseline study staff participant qualitative interview can be found in Section 10.12.

The first two questionnaires will take about 15 minutes to complete. The final questionnaire will take about 25 minutes to complete. Staff study participants will be asked to answer the questions at Month 1 based on their current expectations of administering the injection, and at the following timepoints based on their current experience administering the injection. The Month 12 assessment will include the CSAT, which may be scheduled in a separate assessment period to ensure thorough completion and support for sites following the conclusion of the study.

With notification or approval by the study team, timing and format of interviews and questionnaires maybe adjusted during times of exceptional circumstances as a result of COVID-19, missed visit. etc.

Details about concepts measured in the staff study participant questionnaires can be found Section 10.11.

Patient Qualitative Interviews and Quantitative Questionnaires:

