9. STATISTICAL CONSIDERATIONS

9.1. Statistical Hypotheses

The hypotheses on the quantitative aspects of this study is that enhanced implementation strategy is superior than the standard implementation strategy in terms of mean staff study participant (SSP) AIM/IAM/FIM scores. i.e.,

 H_0 : μ (enhanced) = μ (standard) vs. H_1 : μ (enhanced) > μ (standard)

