9.2. Sample Size Determination

The study size is based on practical considerations in terms of feasibility of enrolling an adequate number of sites on each implementation strategy balanced with the desire to have interventions tested across several types of investigative sites; as well as enrolling an adequate number of patient study participants in each site.

Approximately 24 sites (from feasibility process) will be selected from the feasibility process to achieve 18 sites randomly assigned to study implementation strategies and approximately 54 evaluable staff study participants for an estimated total of 27 evaluable study staff participants per implementation strategy group.

Assuming 10% screen failures, it is estimated that with 18 sites approximately 527 patient study participants will be screened to achieve 474 subjects enrolled and 450 evaluable patient study participants completing the study (assumes 5% of patient study participants would be non-evaluable) for an estimated total of 225 evaluable patient study participants per implementation strategy group.

Power to Show Superiority in mean SSP AIM/IAM/FIM scores

Table 10 shows preliminary AIM/IAM/FIM data from the ongoing U.S. implementation study CUSTOMIZE (209493).

	N	Mean	SD	Median	Observed Range (min-max)	Floor n (%)	Ceiling n (%)	Skewness	Kurtosis
AIM Scale (Total Sample)	24	4.39	0.61	4.13	3.25-5.00	0 (0.0%)	11 (45.8%)	-0.16	-1.58
IAM Scale (Total Sample)	24	4.45	0.59	4.50	3.25-5.00	0 (0.0%)	12 (50.0%)	-0.34	-1.39
FIM Scale (Total Sample)	24	4.32	0.71	4.25	3.00-5.00	0 (0.0%)	11 (45.8%)	-0.47	-1.09

Table 10Staff Study Participants Scores at Month 4 in CUSTOMIZE (209493)

Based on these preliminary data from CUSTOMIZE study, and the given sample size (the number of study participants), the power to detect a difference of 0.5 between the implementation arms in terms of AIM, IAM and FIM are shown in Table 11.

Table 11 Power to Detect a 0.5 Difference in AIM/IAM/FIM

Endpoint	ARM-S	ARM-E	Delta	SD	Alpha	N(S)	N(E)	Power*
AIM	4.39	4.89	0.5	0.61	0.05	27	27	84%
						36	36	93%

Endpoint	ARM-S	ARM-E	Delta	SD	Alpha	N(S)	N(E)	Power*
IAM	4.45	4.95	0.5	0.59	0.05	27	27	86%
						36	36	94%
FIM	4.32	4.82	0.5	0.71	0.05	27	27	72%
						36	36	84%

*Power calculation using two-sided t-test assuming equal variance.

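### The primary staff endpoint is change from baseline, but the hypothesis, comparison and power are on unadjusted mean scores, and no supplied document adjusts for the Month 1 score the trial collects

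*Protocol*

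**What the plan says.** Protocol section 9.4.1 defines the primary staff endpoint as a change; the entry begins "Change from baseline at Month 12 in Acceptability of Intervention Measure (AIM" and goes on to the other two scales. The method column gives descriptive summaries: "Data will be summarized by month of study/injection visit and by implementation strategy as actual values and change from baseline". The between-arm step is "Mean AIM, IAM and FIM scores will be compared between the two implementation arms", with p-values. It names no model, test or covariate, and does not say whether the means compared are Month 12 scores or changes.

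Section 9.1 states the hypothesis on scores: the enhanced strategy is "superior than the standard implementation strategy in terms of mean staff study participant (SSP) AIM/IAM/FIM scores". The footnote to Table 11 in section 9.2 reads "Power calculation using two-sided t-test assuming equal variance", and the SDs in that table are those of raw scores at Month 4 of the US reference study (Table 10). Later in section 9.2, however, the precision calculation for the provider population is built on paired changes from baseline.

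Staff complete the scales at Months 1, 5 and 12 (Protocol Table 2 and section 4.2.5). At Month 1 they "answer the questions at Month 1 based on their current expectations of administering the injection"; later they answer from experience.

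SAP section 2.4 defers the analysis of this hypothesis to a separate vendor SAP, and SAP sections 3 and 7 do the same for the implementation outcomes. That document is not among those supplied. The covariates listed in SAP section 5.4.1 do not include a baseline staff score.

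**The concern.** The protocol points to two different tests, and neither makes good use of the Month 1 score. A comparison of raw Month 12 means leaves it out. A comparison of changes subtracts all of it, which adds noise whenever Month 1 and Month 12 scores correlate below 0.5. A modest correlation is plausible here, because the first questionnaire measures expectation and the last measures experience. Adjusting for the Month 1 score has a residual variance no larger than either, at the price of one degree of freedom.

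At stake are the power of a comparison with about 27 raters per arm, in which FIM starts below 80%, and clarity about which quantity the primary p-value tests.

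**Working it through.** **Inputs.** Difference 0.5, two-sided alpha 0.05, 27 per arm, SDs 0.61 (AIM), 0.59 (IAM) and 0.71 (FIM), all from Protocol Table 11. The correlation r between a rater's Month 1 and Month 12 scores is in neither document. It is an assumption here, shown from 0.1 to 0.7. Staff are treated as independent, as in the plan.

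**Method.** Noncentral t power with noncentrality 0.5 / (SD_eff × √(2/27)), where √(2/27) = 0.272.

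- Raw means: SD_eff = SD, 52 degrees of freedom.
- Change from baseline: SD_eff = SD × √(2(1 − r)), 52 degrees of freedom.
- Adjusted for Month 1: SD_eff = SD × √(1 − r²), 51 degrees of freedom.

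**Plan's own figures.** The raw-mean calculation gives 84.0%, 86.3% and 71.9% at 27 per arm, and 92.9%, 94.4% and 83.8% at 36 per arm. Table 11 states 84%, 86%, 72% and 93%, 94%, 84%. The planned power is therefore that of an unadjusted two-sided t-test on raw scores.

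**FIM at r = 0.3, in full.** Raw: 0.5 / (0.71 × 0.272) = 2.59, power 71.9%. Change: SD_eff = 0.71 × √1.4 = 0.840, noncentrality 2.19, power 57.4%. Adjusted: SD_eff = 0.71 × √0.91 = 0.677, noncentrality 2.71, power 75.8%.

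**All scales, 27 per arm, power in %**

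| r | AIM raw / change / adjusted | IAM raw / change / adjusted | FIM raw / change / adjusted |
|---|---|---|---|
| 0.1 | 84.0 / 59.6 / 84.4 | 86.3 / 62.5 / 86.7 | 71.9 / 47.3 / 72.3 |
| 0.3 | 84.0 / 70.5 / 87.2 | 86.3 / 73.3 / 89.3 | 71.9 / 57.4 / 75.8 |
| 0.5 | 84.0 / 84.0 / 92.7 | 86.3 / 86.3 / 94.1 | 71.9 / 71.9 / 83.4 |
| 0.7 | 84.0 / 96.8 / 98.5 | 86.3 / 97.6 / 99.0 | 71.9 / 90.6 / 94.5 |

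The variance of the change estimate relative to the adjusted one is 1.4 / 0.91 = 1.54 at r = 0.3 and 1.0 / 0.75 = 1.33 at r = 0.5.

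**Chance baseline gap.** If the baseline SD equals the Month 4 reference SD, the standard error of the arm difference at Month 1 is SD × 0.272: 0.166 (AIM), 0.161 (IAM) and 0.193 (FIM). A raw Month 12 comparison inherits r times the gap. For a gap of one standard error that is 0.3 × 0.161 to 0.3 × 0.193 = 0.05 to 0.06 at r = 0.3, and 0.5 × 0.161 to 0.5 × 0.193 = 0.08 to 0.10 at r = 0.5. A change-score comparison errs the other way, by (1 − r) times the gap: 0.7 × 0.161 to 0.7 × 0.193 = 0.11 to 0.14 at r = 0.3.

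**Is Month 1 a true baseline?** By the footnotes to Protocol Table 2, Month 1 starts at site activation and the questionnaire need only precede the site's first injection. The initial SWAT meeting, given only in the enhanced arm, falls within four weeks of activation. In-person injection training, also for that arm only, comes before the first injection (Table 6). A first injection follows screening and about one month of oral lead-in (section 4.3.3). A Month 1 score can therefore be collected after enhanced-arm support has begun.

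**The case against.** A reader might infer that the primary comparison ignores each rater's Month 1 score. The documents do not support that: the score enters the endpoint definition, the planned summaries and the provider precision calculation. They leave open which means are tested. The detailed method is also deferred to an unseen SAP, so all that can be said is that no supplied document specifies an adjustment.

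A reader might also infer that a baseline gap of a third of the 0.5 target (0.16 to 0.19) would be read as a strategy effect. That does not follow either. Only r times the gap reaches a raw Month 12 comparison. Under randomisation the unadjusted test is unbiased, and its standard error already allows for chance imbalance.

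The gain may be small. At r = 0.3 adjustment adds about 3 to 4 points over raw means, and at r = 0.1 under half a point. In the reference study 46% to 50% of staff were at the ceiling (Table 10), so the SD multipliers are rough.

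Adjustment has its own hazard. If Month 1 scores follow enhanced-arm contact, forcing a common baseline mean, or adjusting for such a score, could absorb part of the strategy effect. Section 4.3.2 also expects staff turnover, and replacements may have no Month 1 score. An adjusted Month 12 analysis drops them while a longitudinal model keeps their later scores, so the two are not interchangeable.

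All of this stands, and it limits the claim and shapes the fix. It does not remove the mismatch between a change endpoint and a comparison powered on raw means, or supply a baseline adjustment.

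**Conclusion.** The point holds in limited form. The endpoint is a change, the hypothesis and power are on raw means, and no baseline adjustment is specified in the documents seen. If raw means are tested, the loss in FIM power against adjustment is about 4 points at r = 0.3 (72% against 76%) and about 11 to 12 points at r = 0.5 (72% against 83%). If changes are tested, FIM power at r = 0.3 is 57%, about 15 points below the stated 72%. That 57% is not a finding about the trial's actual power, since it depends on an assumed r and on an unsettled reading.

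The figures also assume equal SDs at Months 1 and 12, the reference-study SDs, and independent staff within sites. Within-site correlation, a separate matter, would lower these power figures and widen the chance baseline gap.

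**What to change.** State as primary, in Protocol section 9.4.1 and the vendor SAP, the arm difference in Month 12 score adjusted for the rater's own Month 1 score, with a site random effect because sites are randomised (Protocol section 6.3), reported with its 95% interval. Keep raw means and changes as descriptive summaries.

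Add three conditions:

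- Use as baseline only Month 1 scores completed before arm-specific contact (the SWAT meeting or face-to-face injection training).
- Do not impose a common baseline mean across arms unless that timing holds.
- State how replacement staff without a Month 1 score are handled.

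If the vendor SAP already contains this, citing it and aligning the protocol wording closes the point.

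The cost is wording, one extra model parameter and attention to when the Month 1 questionnaire is completed. The scores are already scheduled for collection. The downside is little gain if the correlation proves low.

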9.4.2. Secondary Endpoint(s)

Endpoints	Statistical Analysis Methods
Staff Study Participants (SSP)	
Change of Implementation Leadership Scale (ILS), Change and Implementation Climate Scale (ICS) over time assessed quantitatively via questionnaires through Month 12	Implementation Leadership Scale (ILS), and Implementation Climate Scale (ICS) will be summarized using descriptive statistics including 95% confidence intervals. Data will be summarized by month of study as actual values and change from baseline.
	Responses will also be summarized overall and by site type. Exploratory analyses will be undertaken to assess the variability of responses by factors including but not limited to site type, setting and for subject level outcomes markers of demographic and baseline characteristics.
FRAME-IS outcome Months 2 – 12 (monthly)	Responses from the FRAME-IS outcome will be summarized by month.
Patient Study Participants (PSP)	
Length of patient study participant visit from arrival until departure from clinic assessed at Dose 1,Dose 2, Dose 4, and Dose 5.	The length of patient study participant visit will be determined from the time of arrival to time of departure and summarized using descriptive statistics including 95% confidence intervals.
Change in Acceptability of Intervention Measure (AIM) Score, Intervention Appropriateness Measure (IAM) Score, and Feasibility of Intervention Measure (FIM) Score over time. Assessed via questionnaires at Dose 7. ^b	Acceptability of Intervention Measure (AIM), Intervention Appropriateness Measure (IAM), and Feasibility of Intervention Measure (FIM) will be summarized using descriptive statistics including 95% confidence intervals. Data will be summarized by month of study/injection visit and by implementation strategy as actual values and change from baseline. Mean AIM, IAM and FIM scores will be compared between the two implementation arms. In addition, distribution of AIM, IAM and FIM items scores will also be compared. P-values will be reported for these comparisons.
	Responses will also be summarized overall and by site type. Exploratory analyses will be undertaken to assess the variability of responses by factors

Endpoints	Statistical Analysis Methods
	including but not limited to site type, setting and for subject level outcomes markers of demographic and baseline characteristics.
Study Staff Participants:	
Total score of the Clinical Sustainability Assessment Tool (CSAT) at Month 12	Total score of the Clinical Sustainability Assessment Tool (CSAT) will be summarized using descriptive statistics including 95% confidence intervals. Data will be summarized by month of study as actual values and change from baseline.
Percentage of injections occurring within target window from the target date.	Percentage of injections occurring within target window from the target date, will be summarized at Month 12, including 95% confidence intervals
	The patient's 'target date' is determined by their first injection date
Proportion of participants with plasma HIV-1 RNA <50 c/mL over time	The proportion of participants with HIV-1 RNA <50 c/mL, based on the snapshot algorithm, will be summarized at Dose 7, with 95% confidence intervals
	The proportion of participants with HIV-1 RNA >= 50c/mL, respectively, based on the snapshot algorithm, will be summarized at Dose 7, with 95% confidence intervals.
Proportion of participants with confirmed virologic failure (CVF) over time	Summary of proportion of participants with confirmed virologic failure (CVF) over time using the FDA Snapshot algorithm in the ITT-E population
Incidence of treatment-emergent genotypic and phenotypic resistance to CAB and RPV in patient study participants with CVF	Incidence of treatment-emergent genotypic and phenotypic resistance to CAB and RPV in patient study participants with CVF will be summarized at Dose 7, with 95% confidence intervals
Incidence and severity of AEs and SAEs over time and the proportion of participants who discontinue treatment due to AEs over time	Incidence and severity of AEs and SAEs over time, will be summarized, with 95% confidence intervals. Proportion of participants who discontinue treatment due to AEs over time will be summarized.

Endpoints	Statistical Analysis Methods
Preference between CAB + RPV LA and daily oral ART medication (received prior to entering the study) quantitatively assessed via preference questionnaire at Dose 7	The proportion of participants preferences between CAB + RPV LA and daily oral ART medication (received prior to entering the study) with be summarized at Dose 7.
Reported injection site reactions over time	Reported injection site reactions over time will be summarized
Absolute values and changes in laboratory parameters over time	Absolute values and changes in laboratory parameters over time will be summarized, with 95% confidence intervals

